4.2. Secondary Objectives

- 4.2.1 Evaluate the effects of nebivolol as compared to atenolol and placebo on cardiovascular health in subjects with early vascular disease as measured by change in Rasmussen Disease Score (RDS) over a 9 month study period.
- 4.2.2 Evaluate changes in each RDS component over the 9 month study period in all treatment groups.
- 4.2.3 Evaluate the changes in risk factor and biomarker measurements from baseline to 3 and 9 month time points in all treatment groups.
- 4.2.4 Compare the sensitivity of pulse contour analysis and flow-mediated dilation methodologies for measuring functional changes in the endothelium and quantifying endothelial dysfunction.

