9.2 Secondary Endpoints

9.2.1 Change in Rasmussen Disease Score (RDS) from baseline to 9 months after intervention initiation. Each test is scored as 0 for normal, 1 for borderline, and 2 for abnormal. The criteria for normal, borderline, and abnormal has been established on the basis of large public databases. The ten cardiovascular tests provide total scores ranging from 0 (low risk) to 20 (high risk).

9.2.2 Change in each of the CDS components as measured from baseline to 3 and 9 months.

- Blood pressure at rest
- Large artery elasticity
- Treadmill exercise test
- Carotid intima-medial thickness
- Electrocardiogram (ECG)
- Left ventricle ultrasound
- Retinal vasculature
- Microalbuminuria
- NT-proBNP

9.2.3 Change in risk factor and biomarker measurements as measured from baseline to 3 and 9 months.

- Total cholesterol, LDL, HDL, and triglycerides
- hsCRP
- blood glucose

9.2.4 Difference in endothelial function quantification and sensitivity to change between pulse contour analysis and flow-mediated dilation from baseline to 9 months after intervention initiation.

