12.1 Statistical Methodology

The primary analysis of the study is descriptive, to obtain a point estimate and 95% confidence interval of the difference in small artery elasticity (C_2) between nebivolol and atenolol treatment arms and nebivolol and placebo at the end of the observation period (9 months). Point estimates and 95% confidence intervals for the improvement in C_2 within each treatment will also be presented.

Secondary analysis estimating difference in Rasmussen Disease Score (RDS) improvement between the nebivolol and atenolol treatment groups along with nebivolol and placebo groups at the end of the observation period (9 months) will also be completed.

Other secondary analyses include estimates of the associations among changes in RDS as well as risk factor and biomarker measurements from baseline to the 3, and 9 month time points in the two positive comparator groups.

Unpaired t-tests will be used to compare the means of C_2 (small artery elasticity) as well as all RDS test component and biomarker values for each subject group at each time point. Paired t-tests will be used to compare baseline values and values from subsequent time points within one group. A P-value of < 0.05 will be considered statistically significant.

Comparison of sensitivity and variability for C₂ and flow-mediated dilation (FMD) methodologies used in quantifying endothelial function of each group over the 9 month study period will also be included in the secondary analyses. Data will be analyzed within and between test groups with a significance level of $P \leq 0.05$.

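### The comparison of C2 with FMD has no between-method test: the within-group and between-group tests in section 12.1 examine each method separately and cannot show that one is more sensitive

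*Combined protocol and SAP*

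**What the plan says.** Section 4.2 (objective 4.2.4) sets the aim: "Compare the sensitivity of pulse contour analysis and flow-mediated dilation methodologies for measuring functional changes in the endothelium and quantifying endothelial dysfunction". Section 9.2 (endpoint 9.2.4) turns it into an endpoint: "Difference in endothelial function quantification and sensitivity to change between pulse contour analysis and flow-mediated dilation from baseline to 9 months after intervention initiation". Both call for a difference between two methods.

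Section 12.1 states that a comparison of sensitivity and variability for the "methodologies used in quantifying endothelial function of each group over the 9 month study period will also be included in the secondary analyses". It then adds one inferential sentence: "Data will be analyzed within and between test groups with a significance level of" P ≤ 0.05. It defines no sensitivity measure, common scale, within-patient pairing or confidence interval for this comparison.

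The tests named in the section are unpaired t-tests between groups, for C2, the RDS components and the biomarkers, and within-group tests: "Paired t-tests will be used to compare baseline values and values from subsequent time points within one group". FMD is not named in either sentence. Section 3 says that FMD appears less sensitive than C2 to changes related to nitric oxide, and gives the relative sensitivity of the two methods as one reason for measuring both.

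**The concern.** The question is whether two methods are equally sensitive. The named tests answer other questions: whether one method's mean changed within an arm, or whether one method's mean differs between arms. One such test for C2 and one for FMD still do not compare the methods. A result below 0.05 on one and above 0.05 on the other is compatible with equal sensitivity.

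Subtracting raw changes would not help. Section 12.2 gives C2 in ml/mm Hg x 100, while section 8.2 derives FMD from artery diameter, so a common scale has to be defined first.

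At stake is a method claim without a controlled error rate. Because section 3 already expects FMD to be the less sensitive method, a chance result with C2 significant and FMD not could easily be taken as confirmation.

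**Working it through.** **Inputs from the documents.** 25 per arm, difference 3.3, SD 3.57, power 0.9, α = 0.05, and the alternative SD of 3.0 (section 12.2); allocation 1:1:1 (section 6); C2 and FMD both measured at 0, 1, 3 and 9 months in the same patients (study schema).

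**Assumptions.** The documents give no FMD effect, FMD SD or C2-FMD correlation. I take equal standardised effects on both methods (equal sensitivity), correlation 0 to 0.7 between the two changes, normal data, two-sided tests, and the SD in section 12.2 as the SD of the analysed quantity.

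**Step 1: reproduce the plan's figure.** n = 2[(z₀.₉₇₅ + z₀.₉₀) × SD/Δ]² = 2[(1.960 + 1.282) × 3.57/3.3]² = 24.6, so 25 per arm, as stated. A one-sided test would give 21, so the plan's figure is two-sided. The standardised effect is 3.3/3.57 = 0.924, and t-based power at 25 per arm is 0.893.

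**Step 2: what each named test has as its null.**

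| Test | Null hypothesis |
|---|---|
| Paired t-test within an arm | no mean change on that one variable |
| Unpaired t-test between arms | no mean difference on that one variable |
| Needed for 4.2.4 and 9.2.4 | equal standardised effects on C2 and FMD |

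Neither named test has the null in the last row.

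**Step 3: how often equally sensitive methods would disagree.** If each method has power p, the chance that exactly one is significant is 2(p − P(both significant)), which is 2p(1 − p) at zero correlation. At the design effect this is 2 × 0.893 × 0.107 = 0.19; at p = 0.50 it is 0.50; at 1.1 SD (3.3/3.0, p = 0.968) it is 2 × 0.968 × 0.032 = 0.06. Simulated unpaired t-tests on one nebivolol-atenolol contrast, 25 per arm, give:

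| True effect on both methods | Power of each test | Corr. 0 | 0.3 | 0.5 | 0.7 |
|---|---|---|---|---|---|
| 0.924 SD | 89% | 19% | 17% | 14% | 11% |
| 0.8 SD | 79% | 32-33% | 27-28% | 23% | 18% |
| 0.567 SD | 50% | 50% | 40% | 34% | 26% |
| 1.1 SD | 97% | 6% | 6% | 5% | 4% |

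By symmetry half of each figure falls in the direction of C2 significant and FMD not: about 6-10% at 0.924 SD.

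Within-arm paired tests with 25 patients vary more: about 34-50% at a mean change of 0.4 SD (correlation 0 to 0.5), but only about 1% at 0.924 SD.

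**Step 4: a direct contrast under the same conditions.** A z-test on the difference of the two standardised effects, allowing for their correlation, rejects in 5.3-5.7% of trials when the methods are equal, for true effects of 0.4 to 0.924 SD and every correlation tried. A percentile bootstrap by patient rejects in about 7% (correlation 0.3).

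Power is limited. For true effects of 0.92 against 0.46 SD, the z-test has 21%, 27%, 34% and 52% power at correlations 0, 0.3, 0.5 and 0.7. For 0.92 against 0.3 SD, the bootstrap has 46% at correlation 0.3 and 60% at 0.5.

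**The case against.** The strongest reply is that the plan contains no faulty decision rule. Section 12.1 does commit to a comparison of the two methods, and no sentence says that a method will be called more sensitive because it alone reached 0.05. That stands. A reader might infer that the written rule errs several times as often as its nominal 5%, or might count any disagreement across all the arm-level comparisons and reach a much larger figure. The documents support neither reading: both attribute to the plan a rule that it does not state. The percentages above are conditional on discordant P-values being used.

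The size also depends on inputs that the documents do not give. With the smaller SD of 3.0 that section 12.2 expects and the same 3.3 difference, disagreement falls to about 4-6%. It reaches 50% only with power near one half and zero correlation between the two measures. This stands too. The figure near 5% at 1.1 SD arises because both tests are then almost certain to be significant, not because the procedure controls the error of a method claim.

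It may also be said that the phrase about test groups could mean the two methods. The natural reading is treatment groups, since the preceding sentence speaks of each group, and under the other reading the statistic would still be undefined.

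Finally, section 12 describes a Phase II study seeking a preliminary estimate, and this is the last secondary objective. That limits the consequence, and it favours an estimate with an interval over a significance threshold.

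**Conclusion.** The point holds as a mismatch between objective and analysis. The plan asks for a difference between methods and supplies only tests on each method separately, so followed as written it cannot test equal sensitivity. This conclusion follows from the text and needs no numerical assumption.

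The practical size does need assumptions. If discordant P-values were used, equally sensitive methods would be separated on one nebivolol-atenolol contrast in about 11-19% of trials at the design effect, about 26-50% near 50% power and about 4-6% at 1.1 SD. This assumes equal standardised effects, correlation 0 to 0.7 and 25 per arm. The defect is worth correcting but is confined to a secondary objective: the primary C2 estimate and the sample size do not depend on it.

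**What to change.** In section 12.1, replace the P ≤ 0.05 sentence for this objective with a direct paired contrast:

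- For the change from baseline to 9 months, compute the standardised between-arm effect (mean difference divided by the pooled within-arm SD) for C2 and for FMD, in patients with both measurements. Name the arm contrast that carries the conclusion; nebivolol against atenolol is the one on which the sample size is built.
- Report the C2-minus-FMD difference in these effects with a 95% CI from a bootstrap that resamples patients within arm, keeps each patient's C2 and FMD together, and re-standardises in every resample.
- Base any claim of differing sensitivity on that CI, and draw none from one method being significant and the other not.
- Define variability. If the coefficient of variation is used, apply it to measured values, not to changes whose mean may be near zero.

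The standardised between-arm effect is one reasonable metric among several; what matters is that one is fixed in advance and contrasted within patients. It addresses sensitivity to change. The part of objective 4.2.4 on quantifying dysfunction needs its own sentence.

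The cost is a paragraph of text and a short program, with no new visits or patients. There are two downsides. Power is modest at 25 per arm, so the answer will often be inconclusive. The percentile bootstrap is also slightly liberal, at about 7% against a nominal 5%, which should be stated when the interval is reported.

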12.2 Design and Sample Size Justifications

A sample size of 25 subjects per arm will be adequate to detect a difference in small artery elasticity of 3.3 units (ml/mm Hg x 100) between positive comparators when power = 0.9 and $\alpha = 0.05$. This is assuming a standard deviation of ± 3.57 units. This assumption is made based on a previous clinical trial measuring small artery elasticity in patients undergoing anti-hypertensive therapy [14].

Subjects in the previous study were not selected on the basis of C₂ as they are in EVIDENCE. Therefore, it is reasonable to assume that our actual standard deviation will be much smaller than our estimate giving us a conservative population sample of 75. Assuming a smaller deviation of 3.0 (instead of 3.57) we would still have an adequate sample with a dropout rate of 7.6%. If rates of attrition exceed 7.6%, subjects will be replaced

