7. TREATMENT PLAN

7.1 Administration Schedule

Depending on assigned treatment group, subjects will take nebivolol, atenolol, or placebo. Matching medications necessary for maintaining the double-blind nature of the study will be provided by Forest, Inc.

Nebivolol 5 mg will be taken once daily with or without food by mouth for the first month. At the 1 month visit, nebivolol will be increased to 10 mg per day and will be taken for up to 8 months.

Atenolol 25 mg will be taken once daily with or without food by mouth for the first month. At the 1 month visit, atenolol will be increased to 50 mg per day and will be taken for up to 8 months.

Placebo will be taken in the same manner as nebivolol and atenolol treatment groups.

Patients will return to clinic at 1, 3, 6 and 9 months (+/- 1 week) for evaluation and a compliance check.

Patients will be instructed to return all study drug bottles and any remaining tablets to each appointment where subject compliance will be assessed by performing tablet counts.

Patients who demonstrate non-compliance during the study will be counseled regarding proper administration of study medication. In cases of continued and/or extreme non-compliance, study participation may be discontinued.

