7.3 Study Drug Dispensing

Study medications and placebos will be dispensed by the University of Minnesota Medical Center, Fairview Investigational Drug Service (IDS) according to the specified blinded randomization protocol at the baseline, 1 month, 3 month and 6 month visits. Study patients

who drop out prior to the 3 month time point will be replaced by alternate patients who meet study criteria and will not toward overall enrollment goal. Each patient will receive one bottle of study medication or placebo, labeled according to applicable regulatory requirements.

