7.4 Emergency Treatment Unblinding

The IDS pharmacist will have the ability to unblind for individual patients only in case of an emergency where the further treatment of the patient is dependent upon knowing the study medication that the patient has been receiving. In the event of pregnancy, the patient's treatment assignment will be unblinded due to the potential effect of active medication on the developing fetus.

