7.6 Duration of Therapy

Patients will receive protocol therapy for 9 months unless any of the following occurs:

- Patient withdraws consent,
- Continued and/or extreme non-compliance,
- Intercurrent illness that prevents further administration of study drugs,
- Study physician feels study treatment is not in the best interest of the patient,
- Unacceptable adverse events(s).

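### The 9-month C2 comparison in 12.1 uses only subjects with a 9-month value, and replacing randomised dropouts under 7.3 and 12.2 restores the number but not the groups as randomised

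*Combined protocol and SAP*

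**What the plan says.** All references are to the combined protocol and SAP.

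- **Section 6** assigns the arm at enrollment, after consent and confirmed eligibility. Anyone who leaves later is therefore a randomised subject.
- **Section 7.3**: subjects who leave before month 3 "will be replaced by alternate patients who meet study criteria and will not toward overall enrollment goal". A verb is missing; presumably they do not count toward the goal.
- **Section 12.2**: "If rates of attrition exceed 7.6%, subjects will be replaced". It gives no time limit and no denominator.
- **Section 7.1**: "In cases of continued and/or extreme non-compliance, study participation may be discontinued". Section 7.6 also ends study therapy for unacceptable adverse events, among other reasons.
- **Section 12.1** makes the primary analysis descriptive: a point estimate and 95% confidence interval for the 9-month C2 difference, nebivolol against atenolol and against placebo. The only between-arm method is "Unpaired t-tests will be used to compare the means of C_2 (small artery elasticity" and of the other measures, arm against arm at each time point.
- **Section 8.1** schedules C2 at screening and at 1, 3 and 9 months.

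No section names an analysis set, says whether a replaced subject's data are used, says whether C2 is measured after study drug stops, or gives a method for a missing 9-month C2.

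**The concern.** Randomisation makes the arms comparable for everyone randomised. A t-test on 9-month values compares only those who reached 9 months. With two active drugs and placebo, departures for adverse events or non-compliance could differ between arms in number and in kind. If those who leave also differ in C2, the estimate is shifted. A substitute who completes is drawn from the same kind of subject as those who stayed, so refilling an arm to 25 leaves the shift in place while the arm looks complete.

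The primary result is the estimate and its interval, so a shift matters even in a descriptive analysis. With no set named in advance, who is counted would also be settled after the data are in.

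**Working it through.** **1. The plan's own figure.** Inputs from 12.2: difference 3.3, SD 3.57, power 0.9, alpha 0.05 (sidedness not stated; two-sided reproduces the figure). Normal approximation: n = 2 × (1.960 + 1.282)² × 3.57² / 3.3² = 24.6, so 25 per arm. The sample size reproduces. One-sided would give 21.

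**2. What replacement buys.** Two-sided t-test with noncentrality 3.3 / (SD × √(2/n)) and 2n − 2 degrees of freedom:

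| SD | 25 per arm | 23 per arm | Gain |
|---|---|---|---|
| 3.57 | 89.3% | 86.6% | 2.7 points |
| 3.0 | 96.8% | 95.4% | 1.4 points |

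**3. The 7.6% figure.** 25 × (1 − 0.076) = 23.1 per arm, so 12.2 is right that the sample is still adequate at SD 3.0. But 7.6% is not the limit that its inputs imply. At SD 3.0, 90% power needs 18 per arm (normal) or 19 (t-test), so 25 per arm tolerates 1 − 18/25 = 28% or 1 − 19/25 = 24% loss.

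**4. The bias.** In one arm let p be the dropout proportion and g the mean 9-month C2 of completers minus that of dropouts. The mean of all randomised subjects is the completer mean minus p × g, so the completer mean is too high by p × g. For two arms:

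bias = p1 × g1 − p0 × g0

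Substitutes who complete have the completer mean in expectation, so the formula is the same with or without replacement. It is zero when p and g are equal in both arms.

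**5. Size.** The rates and gaps below are assumptions. Take the same gap in both arms and SD 3.57. The standard error is 3.57 × √(2/25) = 1.01 and the interval half-width is 2.03.

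| Dropout | Gap | Bias | Share of 3.3 | Coverage of 95% CI |
|---|---|---|---|---|
| 16% v 4% | 0.5 SD | 0.12 × 1.785 = 0.21 | 6% | 94.5% |
| 16% v 4% | 1 SD | 0.12 × 3.57 = 0.43 | 13% | 92.9% |
| 24% v 8% | 0.5 SD | 0.16 × 1.785 = 0.29 | 9% | 94.1% |
| 24% v 8% | 1 SD | 0.16 × 3.57 = 0.57 | 17% | 91.3% |

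Equal rates alone do not protect. With 15% dropout in both arms but a gap of 0.5 to 1 SD in one arm only, the bias is 0.15 × 1.785 = 0.27 to 0.15 × 3.57 = 0.54.

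**6. Simulation.** Assumed: true difference 3.3, SD 3.57, month 3 to month 9 correlation 0.5 or 0.7, dropout after month 3, enrolment until 25 completers per arm, and the unequal rates of step 5.

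- *Dropout depends on the recorded month-3 C2* (6,000 trials per scenario). The t-test was biased by 0.12 to 0.43, with coverage of 92.6% to 95.1%. A likelihood estimate using the month-3 values of all randomised subjects was biased by −0.01 to 0.03, with the same standard error (0.97 to 1.02 v 0.98 to 1.02).
- *Dropout depends on the unrecorded 9-month C2.* The t-test was biased by 0.25 to 0.60 and the likelihood estimate by 0.13 to 0.43.
- *8% dropout in both arms, driven by month-3 C2.* The t-test bias was 0.00 to 0.03.

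The simulated estimator used months 3 and 9 only, not the full model proposed in the fix, and it does not cover losses before month 3.

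**The case against.** A reader might infer that replacement itself biases the estimate. It does not: step 4 gives the same bias for completers alone. The defect lies in what 12.1 leaves unsaid, and replacement merely fails to repair it.

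A reader might also infer that 7.3 excludes replaced subjects from the analysis. It speaks only of an enrollment goal. That they drop out of the primary estimate follows from a t-test on observed values with no rule for missing ones, not from an explicit exclusion. For the same reason, a replaced subject who did have a 9-month C2 is not clearly in or out.

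It is fair to say that the size rests wholly on assumptions. The documents link dropout to C2 nowhere, give no rates by arm, and call the estimate preliminary. Coverage stays above 91% in every case tried. That limits the weight of the point but does not remove it, since the estimate is what the trial will report.

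It is also fair that the first simulated setting is the model's best case. When dropout followed the unrecorded 9-month value, about half or more of the bias remained. A mixed model is one reasonable choice among several, and no cure for all dropout. A bare statement of the analysis set would close part of the gap, but would still leave the t-test without values for those who left.

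**Conclusion.** The point holds and should be fixed before unblinding. As written, the primary 9-month C2 estimate compares subjects who stayed plus substitutes. Under the assumed unequal dropout the bias is roughly 0.1 to 0.6 units against the 3.3-unit target, with coverage of about 91% to 95%. If dropout is equal and of the same kind in all arms, there is none. Its direction depends on which arm loses more and on how those subjects would have fared.

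A reader might infer that the trial is too small. The documents do not support that: 25 per arm reproduces, and losing two per arm costs under 3 points of power. The 7.6% trigger is a matter for clarification, not a shown error in the sample size.

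**What to change.** Add to 12.1:

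> The primary analysis includes all randomised subjects in the arm assigned, including those replaced under 7.3 or 12.2. The 9-month nebivolol–atenolol and nebivolol–placebo differences and 95% CIs come from a mixed model for C2 at 1, 3 and 9 months with arm by visit, baseline C2 by visit and statin stratum, using every recorded value. The unpaired t-test on subjects with a 9-month C2 is reported beside it, with dropouts and reasons by arm. As a sensitivity analysis, missing 9-month C2 values are multiply imputed and then lowered by 0.5 and 1 SD, in each arm in turn and in all arms.

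Baseline C2 is the value that 8.1 takes at screening. With it as a covariate, the arm contrast is the same for the 9-month level (12.1) and for change from baseline (9.1).

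Also:

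- State that subjects who stop study drug are asked, if they agree, to attend the remaining scheduled C2 measurements. Reconcile 7.1, 7.6 and 7.7 with this. It concerns measurement only, not when treatment stops.
- Cross-reference 12.1 in 7.3.
- Leave the 7.6% trigger as it is, but ask the sponsor to state its denominator and reconcile it with the month-3 rule in 7.3. If the denominator is 75, 7.6% is 5.7 subjects, so the sixth loss (6/75 = 8.0%) would exceed it.

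**Cost.** Text edits and a few extra C2 measurements. Sample size and treatment do not change, and the model mostly uses data already scheduled. Off-drug values may make the estimated difference smaller. The model removes the bias only when dropout depends on recorded values. Subjects lost before month 3 have at most a month-1 C2, and those lost before month 1 add nothing to the model, so the sensitivity analysis is a necessary part of the fix.

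### Does the 7.6% attrition threshold for replacing subjects, which cannot be derived from the stated inputs, undermine the sample size?

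*Combined protocol and SAP*

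**What the plan says.** Section 12.2 sizes the trial: "A sample size of 25 subjects per arm will be adequate to detect a difference in small artery elasticity of 3.3 units". This is for the comparison of the two active arms at 90% power and alpha 0.05, with an SD of 3.57 taken from an earlier trial. It argues that the true SD should be lower, because subjects here are selected on small artery elasticity and those in the earlier trial were not. It then says: "Assuming a smaller deviation of 3.0 (instead of 3.57) we would still have an adequate sample with a dropout rate of 7.6" per cent. The next sentence makes that figure a trigger: "If rates of attrition exceed 7.6%, subjects will be replaced".

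Section 7.3 has a separate rule without any rate. For early withdrawals it reads: "prior to the 3 month time point will be replaced by alternate patients who meet study criteria and will not toward overall enrollment goal" (a verb such as count is evidently missing).

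Section 12.1 defines the main result: "The primary analysis of the study is descriptive, to obtain a point estimate and 95% confidence interval" for nebivolol against atenolol and against placebo at 9 months.

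**The concern.** A threshold that governs replacement would normally be the loss at which the planned power is no longer met, and 7.6% is that loss at neither SD in Section 12.2. At 3.57 there is no margin at all, so a rule that lets some losses go unreplaced appears to use up power the trial does not have. At 3.0 the margin is several times larger than 7.6%.

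The rule is also not fully specified. It gives no denominator and no period. Neither section cites the other, so it is unclear whether early drop-outs replaced under Section 7.3 count toward the rate. At stake would be a trial that drifts below 90% power, and staff applying the rule inconsistently.

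**Working it through.** **Inputs.** From Section 12.2: difference 3.3, power 0.9, alpha 0.05, SD 3.57 or 3.0, 25 per arm, threshold 7.6%. From Section 12.1: unpaired t-test. Sidedness is not stated. Two-sided is assumed because it reproduces the plan's 25; one-sided 0.05 gives 21.

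**The plan's own figure.** Normal formula, n per arm = 2(1.960 + 1.2816)² (SD/3.3)².

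- SD 3.57: n = 24.59, rounded up to 25. The plan's figure reproduces. The noncentral-t solution is 25.59, so 26; t-test power with 25 per arm is 89.3% (normal 90.5%).
- SD 3.0: n = 17.37, so 18. By noncentral t, 18.38, so 19.

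**Tolerable loss from 25 per arm** = 1 − n/25.

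- SD 3.57: 1 − 25/25 = 0% (normal); none by t, since 26 exceeds 25.
- SD 3.0: 1 − 18/25 = 28% (normal); 1 − 19/25 = 24% (t).

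A loss of 7.6% leaves 25 × 0.924 = 23.1 per arm. That gives exactly 90% power only at SD 3.46 (normal) or 3.38 (t), and the plan states neither. One-sided alpha, power 0.8 or 0.95, Bonferroni alpha, inflation by (1 + d) and a three-arm ANOVA do not give 7.6% either.

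**What the threshold permits.**

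- Pooled over 75: 0.076 × 75 = 5.7. Five losses (5/75 = 6.7%) go unreplaced and the sixth (6/75 = 8.0%) triggers replacement.
- Per arm: 0.076 × 25 = 1.9. One loss (1/25 = 4%) goes unreplaced and the second (2/25 = 8%) triggers replacement.

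| Completers in the two compared arms | t-test power, SD 3.57 | t-test power, SD 3.0 |
|---|---|---|
| 25 v 25 | 89.3% | 96.8% |
| 24 v 24 (per-arm limit) | 88.0% | 96.2% |
| 23 v 23 (about 7.6% in each arm) | 86.6% | 95.4% |
| 22 v 23 (five losses split over both) | 85.8% | 95.0% |
| 20 v 25 (five losses in one arm) | 85.4% | 94.8% |

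**Effect on the primary result.** Expected 95% CI half-width = t(0.975, 2n − 2) × SD × √(2/n). At SD 3.57 it is 2.03 units with n = 25 and 2.12 with n = 23, a difference of 0.09 units.

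**The two replacement rules side by side.** Section 7.3 replaces every drop-out before month 3, whatever the rate. Section 12.2 replaces once a rate is exceeded. They do not conflict: the first handles early losses, and the second can take effect for later ones. With Section 7.3 in force, losses left unreplaced can arise only from month 3 onward, so the lower rows of the table require all five losses to be late ones.

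**The case for a change.** The best case for a change is that this number directs conduct. Two coordinators reading Section 12.2 in good faith could act differently, one after the second loss in an arm and the other after the sixth loss overall. Early drop-outs already replaced under Section 7.3 might or might not help cross the threshold. Section 12.2 justifies the sample by power and Section 12.1 keeps a significance rule ("A P-value of < 0.05 will be considered statistically significant"), so the descriptive label does not make power irrelevant. The smaller SD is the plan's expectation and not an observed value; if 3.57 is right, there was never any allowance for drop-out.

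All of that is factually right, and part of it stands: the source of 7.6%, its denominator and its link to Section 7.3 are undocumented. But none of it shows a false statement or a faulty analysis. A trigger may be set stricter than the tolerable limit, and at SD 3.0, the SD to which the plan attaches it, this one is. Either denominator keeps power at 85% or more at SD 3.57 and close to 95% or more at SD 3.0. Restating 7.6% as an expected attrition rate would not be an improvement, because the documents do not say whether it is an expected rate or a tolerance.

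**Conclusion.** No change to the plan is needed. The 7.6% cannot be reproduced, but the sentence that introduces it is true at the SD it names, and the plan nowhere presents it as the largest loss the design can bear. At the less favourable SD of 3.57, losses up to the threshold cost at most about 4 points of power (89.3% to 85.4%, with all five pooled losses in one compared arm). With 23 per arm, they add about 0.09 units to the half-width of the confidence interval. In a Phase II trial whose primary analysis is an estimate with its interval, that does not alter what can be concluded.

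The open details are ones that staff can settle sensibly: replace early drop-outs under Section 7.3, apply Section 12.2 to later ones, and record which denominator is used. The sponsor could note the origin of 7.6% in the trial file, but the design and analysis do not depend on it.

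This rests on two-sided alpha 0.05, equal SDs in the compared arms, and replacement being carried out as Sections 7.3 and 12.2 say. Whether the true SD will be nearer 3.0 than 3.57 is the plan's own expectation and cannot be checked from the documents; the conclusion holds at both values.
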